5 STUDY MEDICATION

5.1 Presentation of Study Drug

Patisiran (ALN-TTR02) Solution for Injection is an RNAi therapeutic consisting of an siRNA targeting TTR mRNA formulated in a LNP. The patisiran drug product is a sterile formulation of TTR siRNA with lipid excipients (DLin-MC3-DMA, DSPC, cholesterol, and PEG₂₀₀₀-C-DMG) in isotonic phosphate buffered saline. Patisiran Solution for Injection contains 2 mg/mL of TTR siRNA drug substance.

The patisiran drug product is packaged in 10 mL glass vials with a fill volume of 5.5 mL. The container closure system consists of a United States Pharmacopeia/European Pharmacopoeia (USP/EP) Type I borosilicate glass vial, a Teflon-faced butyl rubber stopper, and an aluminium flip-off cap.

The control drug for this study will be a placebo (normal saline 0.9% for IV administration). Control drug will be provided by a central supplier.

5.2 Preparation of Study Drug

Each investigational site will be responsible for IV preparation and labeling, according to separate handling instructions, and allocating treatments to the patients.

The pharmacist or unblinded study personnel will prepare the study drug under aseptic conditions. The total amount to be infused into each patient at each dosing visit will be 200 mL. To maintain the blind, all IV infusion bags and lines will have amber-colored covers added prior to leaving the pharmacy.

Additional study drug preparation details are provided in the patisiran (ALN-TTR02) Pharmacy Manual.

5.2.1 Preparation of Patisiran

The amount (in mg) of patisiran to be administered will be determined based on the patient's body weight (kg). For each dose administered, the weight obtained during the previous visit will be used to calculate the dose of study drug. In the event that the weight obtained on the previous dosing day is not available, the weight obtained predose on the dosing day can be used for dose calculation. Patients who weigh 105 kg or more will receive patisiran dosing based on an assumption of a body weight of 104 kg.

Sterile normal saline (0.9% NaCl) will be added to a sterile infusion bag, and the calculated volume of patisiran will be withdrawn from the vials and injected into the infusion bag.

5.2.2 Preparation of Placebo

Normal saline (0.9% NaCl), provided by a central supplier, will be infused into patients randomized into the control group. Depending on the availability, saline may need to be withdrawn from a larger bag or additional saline may need to be added to a sterile infusion bag to ensure the 200 mL volume.

5.3 Drug Administration

5.3.1 Premedication

Prior to each dose of study drug, in order to reduce the risk of experiencing an IRR, patients will receive the following premedications at least 60 minutes prior to the infusion:

- Intravenous dexamethasone (10 mg) or equivalent;
- Oral paracetamol/acetaminophen (500 mg) or equivalent;
- Intravenous H2 blocker (e.g., ranitidine 50 mg, famotidine 20 mg, or equivalent other H2 blocker dose);
- Intravenous H1 blocker: diphenhydramine 50 mg (or equivalent other IV H1 blocker available at the study site). Hydroxyzine or fexofenadine 25 mg per os (PO, orally) or cetirizine 10 mg PO may be substituted for any patient who does not tolerate IV diphenhydramine or other IV H1 blocker.

Patients will be started on the above premedication regimen. However, modifications may be made to the premedication regimen after consultation with the medical monitor either due to a patient's inability to tolerate one or more of the premedications or to the occurrence of IRRs unresponsive to slowing of the infusion rate.

- If a patient is having difficulty tolerating the steroid premedication regimen (e.g., patient develops uncontrolled hyperglycemia, altered mental status, or other complication), then lowering of the steroid premedication may be allowed for that patient after consultation with the medical monitor.
- If after consultation with the medical monitor, it is agreed that an individual patient's steroid premedication will be lowered, then the following steps **must be followed**:
 - 1) If the current steroid dosage is 10 mg intravenous dexamethasone or equivalent, then the patient may be lowered in increments no greater than 2.5 mg intravenous dexamethasone or equivalent.
 - 2) After each incremental lowering below 10 mg intravenous dexamethasone or equivalent, the patient must receive three consecutive intravenous doses of patisiran without IRR and continued signs or symptoms of steroid intolerance before further reductions in steroid premedications.
 - 3) The premedication steroid dosage should not be reduced below 5 mg intravenous dexamethasone or equivalent.

Alternatively, if a patient experiences an IRR when 10 mg or less of intravenous dexamethasone or equivalent is used as the steroid premedication, then proceed to [Section 5.9](#).

Further details (including a table of equivalent premedications) can be found in the patisiran (ALN-TTR02) Pharmacy Manual.

5.3.2 Study Drug Administration

Patients who are randomized into the active treatment group will receive 0.3 mg/kg patisiran once every 21 days (\pm 3 days). Patients who are randomized into the control group will receive placebo (normal saline 0.9%) once every 21 days (\pm 3 days).

The body weight that was obtained during the previous visit must be used to calculate the dose of study drug. In the event that the body weight obtained on the previous dosing day is not available, the body weight obtained pre-dose on the dosing day can be used for the dose calculation. Patients who weigh 105 kg or more will receive patisiran dosing based on an assumption of a body weight of 104 kg.

Study drug (either patisiran or placebo) will be administered under the supervision of the unblinded site personnel, as a 70-minute IV infusion (approximately 1 mL/minute for the first 15 minutes followed by approximately 3 mL/minute for the remainder of the infusion). The study drug will be administered via a controlled infusion device with an extension set containing a 1.2 micron filter supplied by Alnylam or designee. Infusion products must not contain polyvinyl chloride, di(2-ethylhexyl)phthalate (PVC, DEHP). As described in [Section 4.4.3](#), the tubing and the lines will be covered so that it will not be possible to detect a difference in active versus placebo drug.

- If the patient experiences an IRR the infusion time may be extended up to 3 hours in the event of a mild or moderate IRR.
 - 1) If the patient experiences a mild or moderate IRR that resolves by slowing the infusion rate then no further premedication changes are recommended.
 - 2) If the patient experiences a severe IRR, then study drug administration will not be resumed until the case is discussed with the medical monitor (see [Section 5.9](#)).
- If the infusion time for a patient was extended due to an IRR, that modified infusion duration should be continued throughout the duration of the study for that particular patient. Returning the patient's infusion duration to 70 minutes will require a discussion with the medical monitor.
- For the first 3 infusions of study drug on this study, the patient's infusion site should be assessed for signs of any localized reaction during the infusion and for 30 minutes after the end of the infusion, and the patient will remain at the clinical site for 1 hour following completion of dosing.

If a patient does not receive a dose of study drug within the dosing window (\pm 3 days), the dose will be considered missed and not administered.

Additional details can be found in the patisiran (ALN-TTR02) Pharmacy Manual.

In addition, patients will receive an oral daily supplemental dose of the recommended daily allowance of vitamin A.

5.4 Storage of Study Drug

All study drug must be stored in a secure, temperature controlled location and may be dispensed only by a staff member specifically authorized by the Investigator or by a

pharmacist, as appropriate. All study drug will be stored upright and refrigerated at approximately $5 \pm 3^{\circ}\text{C}$. Any deviation from the recommended storage conditions must be reported to the CRO and/or Alnylam and use of the study drug halted until authorization for its continued use has been given by Alnylam or designee.

No special procedures for the safe handling of patisiran are required. An unblinded Alnylam Monitor or designee will be permitted, upon request, to audit the supplies, storage, dispensing procedures, and records.

No study product(s) may be administered to any person not enrolled in the study.

Additional preparation details are provided in the patisiran (ALN-TTR02) Pharmacy Manual.

5.5 Labeling and Packaging of Study Drug

All packaging and labeling as well as the preparation of patisiran and placebo will be in compliance with Good Manufacturing Practice (GMP) specifications, as described in the Manufacture of Investigational Medicinal Products Volume 4 Annex 13, and any other or local applicable regulations.

Study drug labels will include all appropriate local labeling requirements on the vial and external label. Sample labels will be submitted to health authorities, per local country submission requirements.

5.6 Measurement of Patient Compliance

Treatment compliance with study drug administration is dependent on the proper preparation and administration of IV infusions by unblinded study site personnel as well as attendance by the patient to the clinic. Treatment compliance with study drug administration will be verified by unblinded study staff observation. A dose will be considered completed if 80% or more of the total volume of the IV solution has been administered to the patient. Patients will be permitted to miss an occasional dose of study drug. However, if a patient misses 2 consecutive doses, the PI, in consultation with the Medical Monitor, will discuss whether the patient will be able to continue on the study.

Patients failing to complete the 18-month efficacy assessment visit will not be eligible to receive patisiran on the open-label extension study.

5.7 Study Drug Accountability

The Investigator will maintain accurate records of receipt and the condition of all study drugs including dates of receipt. In addition, accurate records will be kept of the weight used to calculate each dispensed patisiran dose, and when and how much study drug is dispensed and used by each patient in the study. Any reasons for departure from the protocol dispensing regimen must also be recorded.

Drug accountability records and inventory will be available for verification by unblinded Alnylam Monitor or designee that will not have a role in any other aspect of managing the study. Remaining study drug (all used, partially used, and unused vials) will be returned to Alnylam or its specified designee/depot or destroyed at the site according to applicable regulations.

Study drug must not be used for any purpose other than the present study. Study drug which has been dispensed for a patient and returned unused must not be redispensed.

Further instructions about study drug accountability are detailed in the patisiran (ALN-TTR02) Pharmacy Manual.

5.8 Concomitant Medication / Treatment

Use of the following medications/treatments is prohibited during study participation (with the exclusion of patients who have rapid disease progression and discontinue study drug after the 9-month efficacy assessments):

- Any investigational agent other than patisiran;
- Tafamidis (use prior to screening permitted);
- Diflunisal (use prior to screening permitted);
- Doxycycline/TUDCA (use prior to screening permitted);
- Corticosteroids other than those administered as premedications prior to the dose of patisiran, those used to treat an infusion reaction, or topical or inhaled corticosteroids. However, for patients with chronic inflammatory disorders (e.g., asthma, rheumatoid arthritis, etc.), systemically administered steroids may be permitted provided that: 1) the dose is <20 mg/day prednisone or equivalent if administered chronically, or 2) for doses \geq 20 mg/day, administration is limited to no more than 5 consecutive days.

Medications and treatments other than those specified above, including palliative and supportive care approved by the investigator for disease-related symptoms, are permitted during the study.

Investigator should review over-the-counter (OTC) and or herbal preparations to ensure that these are not potentially disease modifying.

Use of all concomitant medications and treatments will be recorded on the patient's CRF through the time points shown in [Table 1-1](#), [Table 1-2](#), and [Table 1-3](#). This will include all prescription drugs, herbal preparations, OTC medications, vitamins, and minerals. Any changes in medications during the study will also be recorded on the CRF.

Any concomitant medication or treatment that is required for the patient's welfare may be given by the Investigator. However, it is the responsibility of the Investigator to ensure that details regarding the medication or treatment are recorded on the CRF, and coded using an internationally recognized and accepted coding dictionary.

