4.3 Exclusion Criteria

A patient will be excluded if they meet any of the following criteria at the time of Screening visit:

1. Had a prior liver transplant or is planning to undergo liver transplant during the study period;
2. Has other known causes of sensorimotor or autonomic neuropathy (e.g., autoimmune disease, monoclonal gammopathy, etc.);
3. Has known primary amyloidosis or leptomeningeal amyloidosis;
4. Has known type I diabetes;
5. Has had type II diabetes mellitus for ≥ 5 years;
6. Has vitamin B12 levels below the lower limit of normal (LLN);
7. Has untreated hypo- or hyperthyroidism;
8. Has had a major surgery within the past 3 months or has a major surgery planned during any point of the study period;
9. Has known human immunodeficiency virus (HIV) infection;
10. Has an active infection requiring systemic antiviral or antimicrobial therapy that will not be completed prior to the first dose of study drug administration;
11. Had a malignancy within 2 years, except for basal or squamous cell carcinoma of the skin or carcinoma in situ of the cervix that has been successfully treated;
12. Has a New York Heart Association heart failure classification > 2 ;
13. Had acute coronary syndrome within the past 3 months;
14. Has uncontrolled cardiac arrhythmia or unstable angina;
15. Has a known history of alcohol abuse within the past 2 years or daily heavy alcohol consumption (females: more than 14 units of alcohol per week; males: more than 21 units of alcohol per week [unit: 1 glass of wine [125 mL] = 1 measure of spirits = $\frac{1}{2}$ pint of beer]);
16. Received an investigational agent or device within 30 days of anticipated study drug administration or 5 half-lives of the investigational drug, whichever is longer;
17. Participated in a clinical trial with antisense oligonucleotide, must have completed a 3-month wash-out prior to start of the study drug administration in this study;
18. Is currently taking tafamidis, doxycycline, or tauroursodeoxycholic acid (TUDCA); if previously on any of these agents, must have completed a 14-day wash-out prior to start of study drug administration in this study;

19. Is currently taking diflunisal; if previously on this agent, must have at least a 3-day wash-out prior to start of study drug administration in this study;
20. Had a prior severe reaction to a liposomal product or a known hypersensitivity to oligonucleotides or any component of patisiran (ALN-TTR02);

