2.2. Protocol Deviations

A deviation is considered any departure from the procedures set forth in the protocol. Protocol deviations will be classified into major and minor by medical review and recorded prior to database lock. A major deviation is a deviation that may impact patient safety or efficacy interpretation (for example, failure to meet key inclusion and exclusion criteria). Deviations not designated as major will be considered minor.

The Sponsor or designee will be responsible for producing the final protocol deviation file (formatted as a Microsoft Excel file). This file will include a description of each protocol deviation and whether or not this deviation is classified as a major deviation. In addition, each major deviation will be clearly identified as to whether or not it warrants exclusion from the Per Protocol population, based on the potential impact on the efficacy results according to the judgment of the sponsor. This file will be finalized prior to database lock and unblinding of treatment assignments for all patients.

The following are some examples of key inclusion/exclusion criteria. Failure to meet such criteria may warrant the exclusion from the Per Protocol population:

Inclusion:

1. Have a diagnosis of FAP with documented TTR mutation;
2. Have an NIS of 5 to 130 (inclusive) and a PND score of $\leq 3b$;
3. Have a Karnofsky performance status of $\geq 60\%$.

Exclusion:

1. Had a prior liver transplant or is planning to undergo liver transplant during the study period;
2. Has known primary amyloidosis or leptomeningeal amyloidosis;
3. Has known type I diabetes;
4. Has had type II diabetes mellitus for ≥ 5 years;
5. Received an investigational agent or device within 30 days of anticipated study drug administration or 5 half-lives of the investigational drug, whichever is longer;
6. Participated in a clinical trial with antisense oligonucleotide, must have completed a 3-month wash-out prior to start of the study drug administration in this study.

All protocol deviations and major protocol deviations will be presented in data listings.

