3.7. Initiation of Alternative Treatment for FAP

Rapid progression patients have the option to discontinue study drug, receive alternative FAP treatment, and return for their 18-month efficacy assessment. Non-rapid progressors may also initiate alternative FAP treatment during study, although this would be a major protocol violation. Alternative FAP treatment may confound the efficacy outcome. For the primary analysis of mNIS+7, Norfolk QOL-DN and NIS-W, the assessments collected after alternative FAP treatment (liver transplant or use of tafamidis or diflunisal for more than 14 days) will be

treated as missing. The data post alternative FAP treatment will be included in efficacy listings with a footnote and will also be used in sensitivity analyses as specified.

For all other efficacy endpoints, data collected post alternative FAP treatment will be included in analyses.

A separate listing will be provided for patients who initiate alternative treatment for FAP while on study.

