4.6.7. Prior and Concomitant Medications

Prior and concomitant medications will be coded using the WHO Drug Dictionary (March 2015 or later). Results will be tabulated by ATC and preferred term.

When there are partial or missing dates, imputed dates will be used to determine 1) if a medication is prior or concomitant, and 2) duration of exposure of alternative FAP treatment (tafamidis/diflunisal). Imputed dates will not be presented in the listings.

For medications with partial start or stop dates: the first day/month will be imputed for start date, and the last day/month will be imputed for stop date. For medications with a completely missing start date, the medications will be considered as started prior to the first dose of study drug; medications will be classified as prior, concomitant or both depending on the medication stop dates. For medications with a completely missing stop date, the end of study date will be imputed.

Prior and concomitant medications will be presented in data listings.

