5.6. Censoring Data Post Alternative FAP Treatment

In this SAP V2.0, for the primary analysis of mNIS+7 and Norfolk QoL, the data post alternative FAP treatment will be censored. This censoring rule was not previously specified in the protocol or SAP V1.0. The rationale of adding this censoring rule is to eliminate the potential confounding effect caused by alternative FAP treatment. Sensitivity analyses for mNIS+7 and Norfolk QoL will be conducted including data post alternative FAP treatment.

In SAP V2.1, an update was made to apply the censoring rule to NIS-W as well so that the results will be consistent with the component analysis of mNIS+7.

For all other efficacy endpoints, the data will not be censored since no sensitivity analyses are planned.

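### Rapid progressors may switch to doxycycline/TUDCA or an investigational agent, but the SAP censors only after liver transplant, tafamidis or diflunisal, so some post-switch Month 18 scores stay in the primary MMRM

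*Protocol*

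**What the plan says.** Protocol 5.8 prohibits a list of medications during study participation: "Any investigational agent other than patisiran", tafamidis, diflunisal, doxycycline/TUDCA and most systemic corticosteroids. The exemption is in the sentence that introduces the list, so it covers every item: "with the exclusion of patients who have rapid disease progression and discontinue study drug after the 9-month efficacy assessments". Protocol 4.6 describes what such patients are offered as local standard of care for FAP and names no drugs.

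SAP 3.7 defines alternative FAP treatment as "liver transplant or use of tafamidis or diflunisal for more than 14 days". For mNIS+7, Norfolk QOL-DN and NIS-W, assessments after such treatment are treated as missing in the primary analysis. SAP 4.6.7, which handles partial medication dates, again names only tafamidis and diflunisal. SAP 3.8 keeps all other efficacy data, whether collected before or after study drug was stopped. SAP 5.6 gives the purpose: "The rationale of adding this censoring rule is to eliminate the potential confounding effect caused by alternative FAP treatment".

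**The concern.** The protocol opens more therapies than the SAP censors. Fifteen days of diflunisal removes a Month 18 score, while up to 40 weeks of doxycycline/TUDCA or an investigational agent does not. The SAP gives no reason for the difference.

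Elsewhere the documents treat the omitted therapies as relevant. Protocol 4.3 (exclusion 18) puts doxycycline and TUDCA with tafamidis under one wash-out. SAP 2.2 gives "Received an investigational agent or device within 30 days of anticipated study drug administration" as an example of an entry failure that may warrant exclusion from the Per Protocol population. Protocol 9.2.10 planned to impute the 78-week value for patients who discontinue for rapid progression and did not make this depend on the therapy that followed.

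At stake is a primary estimate that follows neither a consistent censoring rule nor a consistent rule of using all data, with no planned analysis that isolates the mixed part. If the uncensored therapy works, scores from placebo users shrink the treatment difference, and scores from patisiran users enlarge it.

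**Working it through.** **1. The lists side by side**

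| Therapy opened to rapid progressors by Protocol 5.8 | Censored by SAP 3.7? |
|---|---|
| Tafamidis | Yes, if more than 14 days |
| Diflunisal | Yes, if more than 14 days |
| Doxycycline/TUDCA | No |
| Other investigational agent | No |

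Liver transplant is not on the 5.8 list but is censored. Corticosteroids are on the list but are not FAP therapy, so leaving them out is right.

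**2. Where an uncensored Month 18 score goes**

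- Primary MMRM (mNIS+7, Norfolk QOL-DN, NIS-W): included under SAP 3.8.
- MI/ANCOVA (mNIS+7 and Norfolk QOL-DN): only missing values are imputed, so the observed score stays.
- MMRM including data after alternative treatment (mNIS+7 and Norfolk QOL-DN): the score is in both this and the primary analysis, so comparing them shows nothing about it.
- PMM (mNIS+7), placebo: the score stays and also informs imputations that are modelled on placebo data.
- PMM, patisiran: a rapid progressor last dosed on Day 252 and assessed from Day 553 is 553 − 252 = 301 days past the last dose, beyond the 60-day on-treatment limit. SAP 7.1 sets that Month 18 value to missing in the input dataset, restores the value from that same dataset, and then imputes from placebo. Read literally, the score is discarded. The accompanying text also mentions replacement by observed values, so the section is ambiguous.

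**3. Longest uncensored exposure**

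Day 273 to Day 553 = 280 days; 280/7 = 40.0 weeks.

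**4. The plan's own figure**

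Inputs from SAP 3.1 and Protocol 9.1: difference 8.95 points, SD 16, 2-sided alpha 0.05, 154 evaluable patients, 2:1 allocation (103 patisiran, 51 placebo). The noncentral t gives 90.1% power, which agrees with the stated 90%.

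**5. Size if nothing is changed**

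Protocol 1.4 expects fewer than 5% rapid progressors: 0.05 × 200 = 10, so at most 9. The documents give neither uptake nor benefit. I assume k = 1 or 3 placebo users, with 9 as the ceiling, each gaining 4.475 points (half the design effect, rounded to 4.5 elsewhere) to 8.95 points (all of it).

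Shrinkage of the treatment difference = k × gain / 51:

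- k = 1: 4.475/51 = 0.09 to 8.95/51 = 0.18 points
- k = 3: 0.26 to 0.53 points
- k = 9: 0.79 to 1.58 points

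For patisiran users, the shift in favour of patisiran per patient is 4.475/103 = 0.04 to 8.95/103 = 0.09 points. The upper value is 1/103, about 1% of the design effect.

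**6. Size compared with the fix**

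Censoring also costs information. The same t-test with k placebo patients simply dropped (51 − k against 103, difference 8.95) gives the middle column.

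| k | Power, scores dropped | Power, scores kept | Gain from dropping (percentage points) |
|---|---|---|---|
| 1 | 89.7% | 88.9–89.5% | 0.2–0.8 |
| 3 | 88.9% | 86.3–88.3% | 0.6–2.6 |
| 9 | 85.9% | 76.2–84.1% | 1.8–9.7 |

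Dropping costs about 0.4 percentage points per placebo patient at k = 1 (90.1 − 89.7) and at k = 3 ((90.1 − 88.9)/3). MMRM would lose less, because it uses the Month 9 value.

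**The case against.** The SAP's short list matches the treatments that the introductions of both documents describe as used for FAP: transplant, tafamidis and diflunisal. The stratification factor names only the two stabilizers. Doxycycline/TUDCA appears only in eligibility and prohibited-drug lists, and nothing in the documents shows that it works. A shared wash-out is not evidence of disease modification: diflunisal has 3 days, yet it is censored. The SAP 2.2 item concerns use before dosing. An investigational agent is not ordinarily local standard of care, and patients who complete Month 18 can enter the open-label extension, which is a reason not to join another trial. Using off-drug data is the SAP's declared default, so the width of the exception is a judgement.

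Most of this stands as a limit on how often the gap will matter. It does not close the gap: 5.8 lifts the ban on these therapies, and SAP 5.6 states a purpose that the definition does not fully serve.

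Three stronger readings are tempting and are not supported.

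- A reader might infer that such scores remain in every mNIS+7 analysis in both arms. For patisiran patients the PMM appears to remove them, so the one anti-conservative case may be partly covered there.
- A reader might take the fall from 90.1% to as low as 76.2% as the cost of leaving the rule alone. That needs nine rapid progressors, all on placebo, all on an uncensored therapy and all gaining the full design effect. It also ignores the power that censoring itself would cost.
- A reader might think SAP 3.7 is wrong to call alternative FAP treatment in non-rapid progressors a major violation. Protocol 5.8 bans these drugs during study participation for everyone except rapid progressors who stop study drug. Protocol 4.5.1 makes needing one a ground for discontinuation, and 6.3.2 only records later use. The label follows the protocol.

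**Conclusion.** The concern holds, and it is minor. The censoring definition is narrower than the set of therapies the protocol permits after rapid progression. Affected Month 18 scores stay in the primary MMRM for three endpoints and in MI/ANCOVA for two of them, and the existing sensitivity analysis cannot reveal them.

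The expected effect is small. At most 9 of 200 patients are expected to qualify, and only some would take an uncensored therapy. For 1 to 3 placebo users the difference shrinks by 0.09 to 0.53 points, which is conservative. For patisiran users it moves 0.04 to 0.09 points per patient in favour of patisiran. These sizes rest on an assumed gain of 4.5 to 8.95 points each and on assumed uptake; the documents give neither. The plan does not show that the primary conclusion is at risk. The case for acting is consistency with the SAP's own stated purpose, at very little cost.

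**What to change.** Before unblinding, define alternative FAP treatment in SAP 3.7 as liver transplant, or more than 14 days of tafamidis, diflunisal, doxycycline/TUDCA given for FAP, or any investigational FAP agent. Use the same list in SAP 4.6.7. The planned MMRM including data after alternative treatment then covers these cases for mNIS+7 and Norfolk QOL-DN without a new analysis. Restricting doxycycline to use for FAP avoids censoring a patient who takes it for an infection.

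No new data are needed: Protocol 6.3.2 and 6.4 already collect subsequent FAP regimens. Protocol 5.8 and the violation wording in SAP 3.7 can stay as they are.

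The cost is a few more Month 18 values missing and handled under MAR, as already planned after tafamidis or diflunisal. The loss of precision is about 0.4 percentage points of power per placebo patient dropped in the simple t-test, and less under MMRM. The timing matters because widening the rule after unblinding would look data-driven.
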